4.2.2. Key Secondary Estimands

The two key secondary estimands of the study are defined as follows.

Key Secondary Estimand 1:

- Treatment: 0.3 mg and 4 mg of JZP150, and placebo.
- Population: Participants with PTSD (as defined in the eligibility criteria).
- Variable (endpoint): Change in Clinical Global Impression of Severity (CGI-S) from Baseline to Week 12.
- ICEs: The main ICE treatment discontinuation will be addressed by treatment policy (primary strategy) and hypothetical approach (alternative strategy). Other possible ICEs are defined in [Section 7.6](#).
- Population-level summary: The mean change from Baseline to Week 12 in CGI-S for each randomized treatment group and the difference in means between each randomized treatment group compared to placebo.

Key Secondary Estimand 2:

- Treatment: 0.3 mg and 4 mg of JZP150, and placebo.
- Population: Participants with PTSD (as defined in the eligibility criteria).
- Variable (endpoint): Change in Patient Global Impression of Severity (PGI-S) from Baseline to Week 12.
- ICEs: The main ICE treatment discontinuation will be addressed by treatment policy (primary strategy) and hypothetical approach (alternative strategy). Other possible ICEs are defined in [Section 7.6](#).
- Population-level summary: The mean change from Baseline to Week 12 in PGI-S for each randomized treatment group and the difference in means between each randomized treatment group compared to placebo.

4.2.3. Other Secondary Endpoints

Other secondary efficacy endpoints include:

- CAPS-5 total score responder: Percent of participants with $\geq 30\%$ improvement on the CAPS-5 total score from Baseline to Week 12.
- CGI-C responder: Percent of participants who are very much or much improved on the CGI-C at Weeks 4 and 12.
- PGI-S responder: Percent of participants with ≥ 1 unit of improvement on the PGI-S from Baseline to Week 12.
- CAPS-5 total score change from Baseline to Week 4.

Jazz Pharmaceuticals
{Statistical Analysis Plan - Protocol #}JZP150-201-02

[figure not shown]
- Change in functional outcomes measured by the Brief Inventory of Psychosocial Functioning (B-IPF) and Sheehan Disability Scale (SDS) from Baseline to Week 12.
- Change in patient and clinician-reported symptoms of PTSD as assessed by the PTSD Checklist (PCL-5) from Baseline to Weeks 1, 4, 8, and 12.
- Change in patient and clinician-reported symptoms of PTSD as assessed by PGI-S and CGI-S from Baseline to Weeks 1, 4, and 8.
- Change in self-reported sleep problems as measured by the Insomnia Severity Index (ISI) and Pittsburgh Sleep Quality Index (PSQI; with the PSQI-addendum [PSQI-A]) from Baseline to Week 12.
- Change in PTSD symptom clusters (intrusive symptoms, avoidance symptoms, arousal/reactivity symptoms, and negative alterations in mood and cognition) as assessed by the change in the subscales of the CAPS-5 from Baseline to Weeks 4 and 12.
- Change in mood and anxiety as assessed by the change in Patient Health Questionnaire (PHQ-9) from Baseline to Weeks 1, 4, 12 and the change in the Structured Interview Guide for the Hamilton Anxiety Scale (SIGH-A) from Baseline to Weeks 4, 8, 12.
- Change in quality of life from Baseline to Week 12 as measured by the Recovering Quality of Life (ReQoL).

The safety endpoints of this study include:

- AEs
- Vital signs
- Physical examination (PE) [REDACTED]
- 12-lead electrocardiogram (ECG)
- Clinical laboratory tests (chemistry, hematology, urinalysis, [REDACTED]
[REDACTED])
- Columbia Suicide Severity Rating Scale (C-SSRS)
- Withdrawal scale (marijuana withdrawal checklist [MWC])

The PK/PD endpoints of this study include:

- Plasma concentration of Anandamide (AEA), JZP150 and its metabolites.

Jazz Pharmaceuticals
{Statistical Analysis Plan - Protocol #}JZP150-201-02

5. STUDY DESIGN

5.1. Summary of Study Design

This is a 12-week, double-blind, placebo-controlled, randomized, parallel-group, multicenter study of the safety and efficacy of JZP150 in the treatment of adult participants with PTSD. Participants who meet Diagnostic and Statistical Manual of Mental Disorders, 5th Edition (DSM-5) criteria for PTSD as confirmed by the Mini International Neuropsychiatric Interview (MINI), with a total PCL-5 score ≥ 33 at Screening and Baseline will be eligible for enrollment.

Approximately 270 participants will be randomized (2:1:2) to receive placebo, 0.3 mg JZP150, or 4 mg JZP150 to ensure that a minimum of 188 participants have 12 weeks of treatment.

Participants will be stratified by the presence or absence of concomitant use of selective serotonin reuptake inhibitor (SSRIs)/ serotonin norepinephrine reuptake inhibitor (SNRIs). The study will consist of the following periods:

- Screening period and washout of prohibited medications (up to 28 days).
- Baseline and randomization (Day -1).
- Double-blind Treatment Period (12 weeks).
- Safety follow-up (2 weeks).

[figure not shown]
The timing and number of administrations of the CAPS-5 has been carefully considered to address the high placebo response rate that has been observed in previous PTSD trials with sertraline and paroxetine ([Hodgins et al 2018](#)). Due to the therapeutic alliance that occurs with the administration of the CAPS-5, and the effect this can have on an already high placebo response rate, our CAPS-5 administration schedule aims to minimize the number of CAPS-5 administrations during the study and to maximize the time between administrations. For this reason, the CAPS-5 is conducted only at Baseline and end of Weeks 4 and 12.

Another important design feature is that if study intervention is permanently discontinued, the participant will be requested to remain in the study and be asked to complete a 12-week efficacy follow-up to collect efficacy and safety data. Every effort will be made to have the participant attend an early discontinuation visit and the Week 12 efficacy follow-up. For those participants who discontinue study intervention prior to Week 4, every effort will be made to have the participant complete the efficacy follow-up at Week 4 and Week 12. The study protocol specifies analysis windows of $+$ /- 4 weeks for the Week 4 and Week 12 visits. Therefore, the protocol intends for efficacy data to be collected at an early discontinuation visit and efficacy follow-up visits, regardless of any ICE, such as early discontinuation from treatment, allowing for the analysis of the primary, key secondary, and other secondary estimands using the treatment policy.

The schema of study is shown in Figure 1.

Jazz Pharmaceuticals
{Statistical Analysis Plan - Protocol #}JZP150-201-02

Figure 1: The schema of study

Abbreviations: QD=Once daily.

Jazz Pharmaceuticals
 {Statistical Analysis Plan - Protocol #}JZP150-201-02

5.2. Study Intervention

The study interventions planned for use in this study are described in Table 1 below.

Table 1: Study Intervention

Treatment Arm	Intervention/Treatment Name	Formulation	Unit Dose Strength(s)	Dosage Level(s)	Route of Administration	Use	Sourcing	Packaging	Labeling	Storage Conditions
1	Placebo	Capsule	Placebo	QD	Oral	Placebo	Provided centrally by the Sponsor	Bottles with 30 capsules/bottle	Double-blind	[REDACTED]
2	JZP150	Capsule	0.3 mg	QD	Oral	Experimental	Provided centrally by the Sponsor	Bottles with 30 capsules/bottle	Double-blind	[REDACTED]
3	JZP150	Capsule	4 mg	QD	Oral	Experimental	Provided centrally by the Sponsor	Bottles with 30 capsules/bottle	Double-blind	[REDACTED]

Abbreviations: mg = milligram; QD = once daily

Jazz Pharmaceuticals
{Statistical Analysis Plan - Protocol #}JZP150-201-02

5.3. Power and Sample Size Calculations

Approximately 270 participants will be randomized (2:1:2) to receive placebo, 0.3 mg JZP150, or 4 mg JZP150.

The sample size was determined based on ensuring at least 80% marginal power to detect a difference of 6 between placebo and each dose of JZP150 for the change in CAPS-5 total score from Baseline to Week 12 ([Stefanovics et al 2018](#); [Stein et al 2006](#)). The sample size for the estimated 70% of evaluable participants completing the 12-week dosing period for each arm (placebo [$n = 75$], 0.3 mg JZP150 [$n = 38$], and 4 mg JZP150 [$n = 75$]) provides a marginal power of 93.4% and 80.9% for comparing the high dose vs placebo and low dose vs placebo, respectively. Calculations are based on assuming a common standard deviation of 10.5, using a two-sample t-test, and two-sided significance level of 0.05. To account for a 30% dropout, a total of 270 participants will be randomized to ensure that a minimum of 188 participants have 12 weeks of intervention data.

5.4. Randomization and Blinding

All participants who sign the informed consent form (ICF) will receive a participant number. The participant number identifies the participant for all study procedures that occur throughout the study. This number is unique and once assigned cannot be reassigned to another study participant.

Treatment allocation/randomization for this study will occur centrally through the use of an interactive response technology (IRT). Following screening, eligible participants will be randomized (2:1:2) to one of three treatment arms: placebo, JZP150 0.3 mg QD, or JZP150 4 mg QD. Randomization will be stratified based on presence versus absence of use of a stable SSRI/SNRI at Screening. The sponsor, CRO, study investigators, clinical raters, and participants will be blinded to treatment assignment.

A double-blind approach will be used throughout the 12-week treatment period. During the study, the number of capsules taken each day will be the same for participants randomized to each treatment, and JZP150 and placebo capsules will look and feel identical.

The IRT will be programmed with blind-breaking instructions. In case of an emergency, the investigator has the sole responsibility for determining if unblinding of a participant's intervention assignment is warranted. Participant safety must always be the first consideration in making such a determination. If the investigator decides that unblinding is warranted, the investigator should make every effort to contact the sponsor prior to unblinding a participant's intervention assignment unless this could delay emergency treatment of the participant. If a participant's intervention assignment is unblinded, the sponsor must be notified within 24 hours after breaking the blind. The date and reason(s) that the blind was broken must be recorded in the source documentation and case report form, as applicable. The participant's treatment assignment may be unblinded for regulatory reporting purposes. Notification of the treatment assignment is only made known to those who require it for safety reporting and submission processes. All other individuals involved in the study, including the investigator (with the

Jazz Pharmaceuticals
 {Statistical Analysis Plan - Protocol #}JZP150-201-02

exception noted above), will remain blinded to treatment assignment. Participants for whom the blind is broken for this reason will not be withdrawn from the study.

Sponsor safety staff may unblind the intervention assignment for any participant with a serious adverse event (SAE) considered related to study intervention. If the SAE requires that an expedited regulatory report be sent to one or more regulatory agencies, a copy of the report identifying the participant's intervention assignment may be sent to investigators in accordance with local regulations and/or sponsor policy.

5.5. Interim Analysis

No interim analysis is planned.

6. ANALYSIS SETS

For purposes of analysis, the following populations are defined in Table 2.

Table 2: Analysis Sets

Analysis Set	Description
Enrolled Analysis Set	The Enrolled Analysis Set includes all participants who provided a signed ICF. This analysis set will be used to summarize participant disposition including number of screened, screen failures, and randomized participants.
Full Analysis Set 1	The Full Analysis Set 1 includes all participants who were randomized and took at least 1 dose of the study intervention, excluding Site 1865*. This analysis set will be the primary analysis set for all efficacy analyses. This analysis set will also be used in the concordance analysis to examine the classification of participants in randomization strata according to different data sources. Participants will be summarized according to the treatment group they were randomized to.
Full Analysis Set 2	The Full Analysis Set 2 includes all participants who were randomized and took at least 1 dose of the study intervention. This analysis set will be used to summarize participant disposition and protocol deviations. This analysis set will also be used in supplementary efficacy analysis. Participants will be summarized according to the treatment group they were randomized to.
Safety Analysis Set	The Safety Analysis Set includes all participants who took at least 1 dose of study intervention. This analysis set will be used to summarize participants' demographic and other baseline characteristics data, past medical conditions/diseases, surgical history, medications, PTSD diagnosis history, exposure to study

Jazz Pharmaceuticals
 {Statistical Analysis Plan - Protocol #}JZP150-201-02

Analysis Set	Description
	intervention, as well as all safety data. Participants will be summarized according to the study intervention they actually received.
Modified Full Analysis Set	The Modified Full Analysis Set includes all participants in the Full Analysis Set 1 who have baseline and at least 1 post-baseline assessment of CAPS-5 total score, CGI-S, or PGI-S score, excluding ineligible participants that were randomized. This analysis set will be used in supplementary efficacy analysis. Participants will be summarized according to the treatment group they were randomized to.
PK Analysis Set	The PK Analysis Set includes all participants who received at least 1 dose of study intervention and have at least 1 post-dose (post first dose) evaluable PK concentration. The PK set will be used to summarize the PK data, demographic and other baseline characteristics data, as well as exposure to study intervention.
PD Analysis Set	The PD Analysis Set includes all participants who received at least 1 dose of study intervention and have at least 1 pre-dose (prior to first dose) and 1 post-dose (post first dose) evaluable PD (AEA) level. The PD set will be used to summarize the PD data.

* Randomized participants from Site 1865 were excluded from this analysis set due to observed serious deviations and significant breaches to the principles of Good Clinical Practice during the study, particularly in the collection of efficacy data. These deviations and breaches are suspected to be gross misconduct and thus considered to have compromised the integrity of the efficacy data collected and reported by this site.

7. GENERAL ASPECTS FOR STATISTICAL ANALYSIS

The statistical principles applied in the design and planned analyses of this study are consistent with ICH E9 guidelines ([ICH 1998](#)).

7.1. General Methods

Data will be listed and summarized according to Clinical Data Interchange Standards Consortium (CDISC) standards. SAS software Version 9.4 or higher (SAS Institute, Inc. Cary, NC) will be used to perform all data analyses, generate tables, figures, and listings.

Categorical variables will be presented using counts and percentages. Unless otherwise specified, continuous data will be summarized using descriptive statistics comprising of the number of participants with data to be summarized (n), mean, standard deviation (SD), median, minimum (Min) and maximum (Max).

For quantitative measurements, change from baseline will be calculated as:

- Change from baseline = Test value at visit X – baseline value

Jazz Pharmaceuticals
 {Statistical Analysis Plan - Protocol #}JZP150-201-02

7.2. Baseline and Study Day Definitions

7.2.1. Baseline

For the study assessments that are either clinician-reported or patient-reported outcomes (CAPS-5, CGI-S, CGI-C, PGI-S, PCL-5, B-IPF, ReQoL-10, SDS, PSQI, PSQI-A, ISI, PHQ-9, SIGH-A, MWC, and C-SSRS), the baseline value is defined as the initial value obtained on the date of the Baseline Visit (Day -1). If this value is missing, the last non-missing value obtained prior to the first dose of study intervention will be used as the baseline value. Repeat assessments performed on the same Baseline Visit date will be included in the clinical database as unscheduled assessment but will not be utilized for analyses. If the scheduled Baseline Visit occurred on the same day (Day 1) of first dosing, the assessment of the above-mentioned endpoints should be considered prior to first dosing.

For all other assessments, the last non-missing value obtained prior to the initiation of study intervention will be used as the baseline value.

7.2.2. Study Day

A study day will be assigned as follows:

- The first dose of study intervention is designated as Day 1. Participants will self-administer the first dose at home the day after the Baseline Visit.
- For visit days after Day 1, study day = visit date - Day 1 date + 1.
- For visit days prior to Day 1, study day = visit date - Day 1 date. Thus, study days for screening visit are negative numbers. There is no “Day 0”.
- The end date of study intervention for each participant is the participant’s last dose date in the study.
- The end date of the study for each participant is defined as the date of the participant’s last assessment, including the safety follow-up and the efficacy follow-up (if the participant stops study intervention) in the study.

7.2.3. Analysis Windows

All scheduled, unscheduled, and early termination assessments will be summarized by derived analysis visit per [Table 3](#), regardless of if the visit was performed on-site or remotely. Visit dates will be mapped based on the scheduled period of each visit, with adjusted analysis-defined windows as specified in [Table 3](#).

Height, serum pregnancy, demographics, medical/surgical history, MINI, C-SSRS (screening/baseline version), and Life Event Checklist for DSM-5 (LEC-5) are only assessed at Screening Visit. The analysis window for these assessments is Day -40 up to -2.

CGI-S, PGI-S, CGI-C, PCL-5, and C-SSRS since last visit will be assessed at efficacy and safety follow-up visits. CAPS-5 will be assessed at efficacy follow-up visits (if applicable) but will not be assessed at the safety follow-up visit. PSQI-A, PSQI, ISI, MWC, and PHQ-9 will be assessed at safety follow-up visit but not at efficacy follow-up visits. AEs and prior/concomitant medications are monitored throughout the study.

Jazz Pharmaceuticals
{Statistical Analysis Plan - Protocol #}JZP150-201-02

A clinic visit at the end of Week 8 is also included for safety assessments, secondary efficacy assessments, sparse PK sampling and study intervention dispensation.

If multiple measurements are recorded within a single analysis window, including unscheduled or repeated assessments, early discontinuation assessments, as well as efficacy and safety follow-up assessments, the following rules will be applied to determine the observation from which assessment will be used for that analysis defined visit.

- If there are two or more observations within the same analysis window, then the non-missing observation closest to the scheduled Visit Day will be used in the analysis.
- If two observations are equidistant from the scheduled Visit Day, the on-treatment observation will prioritize over the off-treatment observation, with the exception for safety follow-up visit. If they are both on-treatment observations, then the non-missing observation with the latest collection date will be used in the analysis.
- If two observations are collected on the same day and this day is the closest to the scheduled Visit Day, for efficacy endpoints, the non-missing observation with the earliest collection time will be used in the analysis; for safety endpoints, the non-missing observation with the latest collection time will be included in the analysis.

Data collected from safety follow-up visit between 7 to 28 days after the last dose can be mapped to the safety follow-up analysis visit. Safety follow-up visits that take place at > 28 days post last dose will be considered out of window and the data collected will not be used.

If an analysis window does not contain any observations, then the data will remain missing for the analysis visit.

Listings will include scheduled, unscheduled, repeated, retest, early termination, efficacy follow-up and safety follow-up data per nominal visits.

Jazz Pharmaceuticals
 {Statistical Analysis Plan - Protocol #}JZP150-201-02

Table 3: Analysis Windows for Assessments or Measurements

Study Period	Scheduled Visit (V)/ Week(W)	Scheduled Visit Day	CAPS-5, SDS ^a	CGI-S, PGI-S, PSQI, PSQI-A ^b , ISI ^b	PCL-5	C-SSRS	CGI-C	MINI, LEC-5, Height, Serum Pregnancy Test	B-IPF ^c , ReQoL-10 ^c , MWC	PHQ-9	SIGH-A ^d , PE	Laboratory, Vital Signs, ECG ^e , Breath Alcohol Test ^e , Urine Drug Screen ^e	Urine Pregnancy Test	Blood Sample PK ^f , AEA, PG ^g
Screening	V1	-40 up to -2	na	na	-40 up to -2	-40 up to -2	na	-40 up to -2	na	-40 up to -2	-40 up to -2	-40 up to -2	-40 up to -2	na
Baseline ^h / Randomization	V2	-1	-1	-1	-1	-1	na	na	-1	-1	-1	-1	-1	-1
Double-Blind Intervention	V3/W1	7±2	na	1-14	1-14	1-7	na	na	1-14	na	1-14	na	1-42	
	V4/W2 (call)	14±2	na	na	na	8-14	na	na	na	na	na	na	na	
	V5/W4	28±2	1-56	15-42	15-42	15-28	1-56	na	na	15-56	1-42	15-42	na	na
	V6/W6 (call)	42±2	na	na	na	29-42	na	na	na	na	na	na	na	na
	V7/W8	56±2	na	43-70	43-70	43-56	na	na	na	na	43-70	43-70	na	43-70
	V8/W10 (call)	70±2	na	na	na	57-70	na	na	na	na	na	na	na	na
	V9/W12	84 (-5, +2)	57-112	71-112	71-112	71-112	57-112	na	1-112	57-112	71-112	71-112	1-112	71-112
Efficacy Follow-up	V11a/W4	28	1-56	1-56	1-56	1-56	1-56	na	na	na	na	na	na	na
	V11/W12	84	57-112	57-112	57-112	57-112	57-112	na	na	na	na	na	na	Na
Safety Follow-up	Safety Follow-up	98(+5)	na	8-112	8-112	8-112	8-112	na	8-112	8-112	na	8-112	8-112	8-112

Abbreviations. AEA = anandamide; B-IPF = Brief Inventory of Psychosocial Functioning; E/D = Early Discontinuation; CAPS-5 = Clinician Administered PTSD Scale version 5; CGI-C = Clinical Global Impression of Change; CGI-S = Clinical Global Impression of Severity; C-SSRS = Columbia Suicide Severity Rating Scale; ECG = Electrocardiogram; ISI = Insomnia Severity Index; LEC-5 = Life Events Checklist for DSM-5; MINI = Mini International Neuropsychiatric Interview; MWC=Marijuana withdrawal checklist; PCL-5 = Posttraumatic Checklist-5; PE=Physical examination; PG=Pharmacogenomics; PGI-S = Patient Global Impression of Severity; PHQ-9 = Patient Heath Questionnaire-9; PK = pharmacokinetics; PSQI = Pittsburgh Sleep Quality Index – PTSD; PSQI-A = Pittsburgh Sleep Quality Index with PTSD Addendum; PTSD = posttraumatic stress disorder; ReQoL = Recovering Quality of Life; SDS = Sheehan Disability Scale; SIGH-A = Structured Interview Guide for the Hamilton Anxiety Rating Scale.

^a SDS is not assessed at efficacy or safety follow-up visits.

^b PSQI, PSQI-A and ISI are not assessed at efficacy follow-up visits.

^c B-IPF and ReQoL are not assessed at safety follow-up visit.

^d SIGH-A is not assessed at screening visit.

^e ECG, breath alcohol test, and urine drug screen are not assessed at safety follow-up visit.

Jazz Pharmaceuticals
{Statistical Analysis Plan - Protocol #}JZP150-201-02

^f Blood sample for PK is not collected at baseline or safety follow-up visit.

^g Blood sample for PG is only collected at baseline visit.

^h For detailed baseline definition, refer to [Section 7.2.1](#).

Jazz Pharmaceuticals
 {Statistical Analysis Plan - Protocol #}JZP150-201-02

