The PK of JZP150 has been characterized in 3 phase 1 studies in a total of 76 healthy adult volunteers after single- (dose range 0.1 to 40 mg) and multiple-dose (dose range 0.5 to 8 mg QD) oral administration. Absorption of JZP150 was rapid, reaching maximal plasma concentrations within an average of 2 hours post dose. Plasma concentrations of JZP150 post maximum plasma concentration (C_{max}) followed a multiphasic decline, with an estimated terminal half-life ($t_{1/2}$) ranging from approximately 12 to 23 hours. The steady-state of plasma concentrations was attained by Day 7 following QD administration for 14 days with an approximate 2 to 3 \times accumulation in exposure between Days 1 and 14. The exposures of JZP150 at steady-state appeared dose-proportional over the dose range of 0.5 to 8 mg following multiple dose administration; but supra-proportional increases in exposure were noted over a similar dose range of 0.1 to 10 mg following single oral administration. Proportional increase of exposures was observed in the dose range of 10 to 40 mg following single dose administration. No major food effects on the PK of JZP150 were observed using a tablet formulation. Examination of the relationship between FAAH inhibition and JZP150 plasma concentration suggests that concentrations of at least 1 ng/mL is required to maintain FAAH inhibition by at least 97%.

JZP150 has been evaluated in 7 sponsor-initiated interventional clinical studies to date. In these studies, a total of 108 healthy volunteers, 37 subjects with osteoarthritis and 8 subjects with PTSD have been administered 4 mg JZP150, which is the high end of the therapeutic dose range. There have been no deaths, serious adverse events (SAEs) or severe adverse events (AEs) in the completed sponsor-initiated interventional clinical studies in subjects who have received JZP150. The overall incidence and severity of AEs observed during these studies has been comparable to placebo. No maximum tolerated dose has been identified. There were no safety concerns suggested by laboratory values, vital signs, or electrocardiogram (ECG) data. Based on this experience, the overall safety and tolerance of JZP150 supports further clinical testing.

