8.7. Biomarkers

Blood samples of approximately 4 mL will be collected to examine plasma AEA concentration at the visits noted in the Schedule of Assessments ([Section 1.3](#)). When AEA draws are taken on days with PK draws, a single 4 mL sample will be drawn for both PK and AEA levels. In addition to being collected at every PK blood sample, AEA will also be drawn at Baseline and at the safety follow-up.

On the days that include PK analysis, the sample will be processed and split into 2 aliquots, one for JZP150 levels and one for AEA levels. At Baseline and safety follow-up, the entire sample (4 mL) will be processed for AEA.

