10.6.4. Marijuana Withdrawal Checklist

The MWC is a 22-item measure developed to assess the incidence and severity of marijuana withdrawal symptoms during the past 2 weeks. The MWC score is derived from the 22 items that are each rated on a 4-point scale from 0 (none) to 3 (severe). The MWC score ranges from 0 to 66 and is assessed at Baseline, end of Week 12, and safety follow-up visit.

Observed and change from baseline values for the MWC score will be summarized by treatment group and pooled JZP150 treatment groups by scheduled visit.

Jazz Pharmaceuticals
{Statistical Analysis Plan - Protocol #}JZP150-201-02

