12. PHARMACODYNAMIC/BIOMARKER ANALYSES

Pharmacodynamic markers (e.g., AEA concentration) will be measured and descriptive statistics including the number of participants, mean, SD, Min, median, Max, %CV, geometric mean, and geometric SD will be used to summarize AEA levels by visit and treatment group. The Pharmacodynamic Analysis Plan may be provided in a separate document.

The pharmacodynamic-response analysis may be conducted and reported separately.

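### Safety follow-up records taken about 14 days off drug can be tabulated as Week 8 or Week 12 AEA values and as Week 12 MWC scores in early stoppers

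*SAP*

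**What the plan says.** SAP 7.2.3 maps all scheduled, unscheduled and early-termination assessments to the analysis windows of Table 3. Where one window holds several records, the candidates include "early discontinuation assessments, as well as efficacy and safety follow-up assessments, the following rules will be applied". The basic rule is: "then the non-missing observation closest to the scheduled Visit Day will be used in the analysis". For two equidistant records, "the on-treatment observation will prioritize over the off-treatment observation, with the exception for safety follow-up visit".

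The section also says: "Data collected from safety follow-up visit between 7 to 28 days after the last dose can be mapped to the safety follow-up analysis visit". SFU data later than 28 days after the last dose are not used. The sentence permits mapping to the SFU visit but does not say that this is the only visit to which SFU data may go.

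SAP Table 7 (section 9.2.2) sends SFU scores of CGI-S and PGI-S to treatment weeks and cites the windowing rule of 7.2.3 as its authority. No corresponding text exists for AEA or MWC.

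On sampling, Protocol 8.7 has AEA taken with every PK sample and adds: "AEA will also be drawn at Baseline and at the safety follow-up". The Schedule of Activities (SoA) shows no AEA draw at early discontinuation (E/D). SAP 10.6.4 says the MWC "is assessed at Baseline, end of Week 12, and safety follow-up visit"; the SoA also places it at E/D. SAP 12 will "summarize AEA levels by visit and treatment group", and SAP 10.6.4 summarises MWC by scheduled visit.

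**The concern.** Letting SFU records into treatment weeks suits endpoints analysed under treatment policy, where off-drug data are wanted. AEA and MWC have a different purpose. AEA shows the pharmacodynamic effect while on drug, and the dose rationale in Protocol 4.3 is framed around plasma AEA above 2 to 2.5 ng/mL. For MWC, the contrast of interest is between the end of dosing and the period after it.

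If SFU records represent Week 8 or Week 12, those rows mix on-drug and off-drug values under one label. For MWC the rule does more than fill a gap: it can replace a score actually taken at stopping. The same SFU record can then appear in both the Week 12 row and the SFU row.

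**Working it through.** **Inputs**
- Table 3 windows: AEA Week 8 = Days 43-70; AEA Week 12 = Days 71-112; MWC Week 8 = not applicable; MWC Week 12 = Days 1-112; SFU = Days 8-112 for both. Targets are Days 56, 84 and 98.
- SoA: Week 8 visit ±2 days, Week 12 visit -5/+2 days, SFU 14 days after last dose with up to 5 days more.
- SAP 5.3: 270 randomised 2:1:2, 30% dropout.

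**Step 1. Reproduce the plan's SFU window.** First dose Day 1 + 7 = Day 8; planned last dose Day 84 + 28 = Day 112. This matches Table 3. The window therefore overlaps almost every treatment week.

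**Step 2. AEA.** Let L be the last-dose day, with SFU on Day L+14.
- Week 8: 43 ≤ L+14 ≤ 70 gives L = 29 to 56. A participant still dosing on Day 54 can have had the Week 8 draw (Days 54-58), so SFU is normally the only record for L of about 29-53.
- Week 12: L+14 ≥ 71 gives L ≥ 57. A participant still dosing on Day 79 can have had the Week 12 draw (Days 79-86), so SFU is normally the only record for L of about 57-78.
- At L+19 the full ranges become 24-51 and 52-84.

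**Step 3. MWC, Week 12.** With E/D on Day L, SFU wins when |L+14-84| < |L-84|. For L ≤ 70 this always holds. For L > 70 it requires L-70 < 84-L, that is L < 77. SFU therefore wins for L = 1 to 76, with a tie at 77. At L+19 it wins for L = 1 to 74.

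**Step 4. Completers.** A Week 12 visit on Days 79-86 is at most 5 days from Day 84. With last dose on Day 79, SFU falls on Day 93, 9 days away; with last dose on Day 84 it is 14 days away. The on-drug value wins unless it is missing.

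**Step 5. Share of off-drug records.** Assume 81 of 270 stop (30%), stop days are uniform over Days 1-83, a fraction *a* attends SFU, completers all have values, and all early stoppers have an E/D MWC.
- AEA Week 8: off-drug = 81 × 27/83 × *a* = 26.35*a* (L = 29-55). On-drug = 189 + 81 × 28/83 = 216.33. At *a* = 1: 26.35/242.68 = 10.9%. At *a* = 0.25: 6.59/222.92 = 3.0%.
- AEA Week 12: off-drug = 26.35*a* (L = 57-83); on-drug = 189. At *a* = 1: 26.35/215.35 = 12.2%. At *a* = 0.25: 6.59/195.59 = 3.4%.
- MWC Week 12: off-drug = 81 × 76/83 × *a* = 74.17*a*, out of 270. At *a* = 1: 27.5%. At *a* = 0.25: 6.9%.

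A check with the narrower AEA ranges, counting later stoppers as sampled on drug:
- L = 29-53 gives 24.40/(218.28 + 24.40) = 10.1% at full attendance.
- L = 57-78 gives 21.47/(193.88 + 21.47) = 10.0%.
- Both give 2.7% at *a* = 0.25.

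With full attendance and dropout of 20% to 40%, the three shares are 7.0-15.0%, 7.5-17.8% and 18.3-36.6%. In a 4 mg arm of 108 (270 × 2/5), 30% dropout gives 2.6 to 10.5 off-drug AEA records at each week and 7.4 to 29.7 off-drug MWC records, across the attendance range.

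**Step 6. What cannot be computed.** The terminal half-life is given as "ranging from approximately 12 to 23 hours". Fourteen days is 336 h, so 336/23 = 14.6 to 336/12 = 28 half-lives. That describes clearance of drug from plasma. JZP150 inhibits FAAH irreversibly, and the documents give neither a FAAH recovery time nor an off-drug AEA level. If AEA were back at placebo level by SFU, which is an assumption, the mean 4 mg minus placebo difference would shrink by the AEA shares above.

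**The case against.** The best counter-argument is that the SAP means to keep SFU data apart. Table 3 gives SFU its own row, and 7.2.3 defines eligibility for it by days since last dose. Because the SFU window spans Days 8-112, a pure study-day rule would make on-treatment records candidates for the SFU row, so visit origin must play some part. Table 7 covers only CGI-S and PGI-S.

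This has force: the text is not fully explicit for AEA and MWC, and a reader who infers that the tables will certainly mix values goes further than the documents do. But Table 7 draws its mapping from 7.2.3 itself, the candidate list names SFU records without restriction by endpoint, and the SFU sentence is only permissive. Two programmers could build different tables, and the plain application of the rule gives the mixed one.

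The objection to size also stands in part. Full SFU attendance is an upper bound, so a range is needed. SAP 7.7 reports limited efficacy data after intercurrent events. That concerns a different visit, but it makes complete attendance doubtful.

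Three stronger inferences are tempting, and the documents do not support them:
- **That the 4 mg AEA elevation will look lost or weaker by a stated amount.** This needs an off-drug AEA level that is not given. The pharmacodynamic objective also relies on population modelling, with actual sampling times recorded, rather than on the by-visit table.
- **That a withdrawal signal will be hidden.** SAP 10.6.4 plans observed values and change from baseline, not a Week 12-to-follow-up change. SFU scores remain in the SFU row. A raised Week 12 mean presupposes that withdrawal occurs.
- **That laboratory and vital-sign windows should accept only on-treatment records.** The same windowing rule covers them, but a blanket restriction goes further than this point requires.

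**Conclusion.** The concern holds as a defect in the mapping rule for two descriptive measures. Applied as written, SAP 7.2.3 allows SFU samples into AEA Week 8 and Week 12, and prefers the SFU score over the E/D score for MWC Week 12 in anyone stopping through Day 76. Under 30% dropout, uniform stopping and 25% to 100% SFU attendance, the off-drug share is roughly 3-11%, 3-12% and 7-27% respectively. These figures illustrate the rule; they are not predictions, and actual dropout timing or differences between arms would change them.

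The effect is limited to the by-visit pharmacodynamic and withdrawal tables, and to early stoppers and participants with a missing Week 12 value. Completers with a Week 12 value are protected. Listings use nominal visits, so affected records can be traced. PK is not sampled at SFU. Primary and key secondary inference does not depend on this point.

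**What to change.** In SAP 7.2.3, with a footnote to Table 3, state that AEA and MWC records collected at the SFU visit map only to the Safety Follow-up analysis visit and are not candidates for any other window. The E/D MWC score then stays as the Week 12 or end-of-treatment value, and AEA is left missing at treatment weeks for participants who stopped before the draw. Keep the present rule for endpoints analysed under treatment policy, such as CGI-S, PGI-S and PCL-5.

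The cost is one sentence, a footnote and a programming flag, with slightly fewer AEA values at Weeks 8 and 12. No new data are needed.
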